- Replacement fluid for the patients in the GDT group will follow **algorithm A. (appendix 1)**
- Postoperatively, all patients will be kept in the PACU until the following morning. Management at this stage will be standardized and equal for both arms:
 - PACU standardized management (algorithm B):
 - Patients requiring continued mechanical ventilation will receive a tidal volume of 8 ml/kg body weight at a frequency of 6 to 12 breaths per minute to keep the end-tidal carbon dioxide between 35 to 40 mm Hg. Most patients will be extubated in the operating room and not require mechanical ventilation.
 - Maintenance IV crystalloid at 1.2 ml/kg/hr with a maximum rate of 130 ml/hr.
 - Strict Inputs and Outputs measured hourly in PACU.
 - Boluses of 250 ml of albumin solution (given over 20 minutes) will be administered for SBP < 90mmHg and/or urine output < 40ml/2hr.

MEMORIAL SLOAN-KETTERING CANCER CENTER IRB PROTOCOL

IRB#: 12-056 A(4)

- Medications mixed as per pharmacy protocol, to be included in daily input.
 - The use of vasoactive agents will be left to the discretion of the treating practitioner.
-
- When patients leave PACU, the arterial line will be removed upon transfer to the floor and fluid management will be as follows:
 - Maintenance IV crystalloid at 1.2 ml/kg/hr (maximum rate of 130 ml/hr) until taking > 400ml/24 hrs po, then d/c.
 - Urine output (UOP) to be maintained at 80ml/4 hours (20ml/hr averaged over 4 hour periods) with boluses of 500 ml crystalloid solution.
 - Lasix 10mg IV starting POD 2 for weight gain greater than 2kg pre operative weight if approved by treating practitioner.
 - If UOP is greater than 60ml/hr over 8 hours, IV rate may be decreased at the discretion of the treating practitioner.

10.0 EVALUATION DURING TREATMENT/INTERVENTION

- Preoperative data will be collected and recorded: date of birth, weight, height, complete metabolic panel, complete blood count, coagulation profile.
- Standard intraoperative monitoring will be carried out for all patients.
- GDT patients will also be monitored by CO, SV and SVV. These data will similarly be obtained and recorded for the patients in the standard management group but it will not be available for the treating practitioners.
- Further measures of end-tissue perfusion will be assessed with arterial lactate levels and DO₂ (oxygen delivery) at baseline (before incision), at completion of the resection phase (intraoperatively), upon arrival to PACU (0 hours postoperatively), and on the morning of POD #1.
- Assessment and recording of all intraoperative and postoperative complications; the latter being considered as those occurring on or after postoperative day 1 until postoperative day 30. Complications occurring intraoperatively and after surgery on

MEMORIAL SLOAN-KETTERING CANCER CENTER
IRB PROTOCOL

IRB#: 12-056 A(4)

the same day, are most likely technical in nature and will be considered perioperative complications in the analysis.

- Estimated operative blood loss.
- Cumulative volume used for resuscitation will be recorded (stratified by colloids and crystalloids)
- Total dose (mcg/kg) of pressors, inotropes or vasodilators used will be recorded and stratified by specific drugs.
- Volume and type of blood products transfused.
- Daily comprehensive metabolic panel, complete blood count (these will be recorded for seven days or until discharged if discharged earlier).
- Daily coagulation panel, discontinued by POD 3 if normal.
- Volume and type of fluid intake and output until POD 7 or patient tolerates oral intake of fluids > 400 ml/24 hrs
- Daily nasogastric tube drainage volume (if used) and length of NG drainage
- Daily weight until POD 7 or until patient tolerates oral intake of fluids > 400 ml/24 hrs.
- Day of tolerating oral intake of fluids > 400ml/24hrs
- Day of IV ≤ KVO
- Day of tolerating oral intake of solids
- Day of passage of flatus
- Day of foley removal.
- Day of passage of feces
- Day of discharge

Table 2. Details hemodynamic and laboratory values obtained at different stages. For laboratory values a 30 minute variation will be allowed to account for early or delayed sample collection in the PACU and/or surgical ward.

	Baseline Preop (pre intubation)	Baseline intraop (after intubation)	Resuscitation Phase	PACU (0 hrs postOp)	4 hrs postOp	8 hrs postOp	12 hrs postOp	Morning of POD 1	Morning of POD 2
Stroke Volume (μ ± SD)	x			x	x	x		x	
*Stroke Volume (μ ± SD)	x								
% change in SV	x								
Stroke Volume Variation- SVV (μ ± SD)		x	x						

MEMORIAL SLOAN-KETTERING CANCER CENTER IRB PROTOCOL

IRB#: 12-056 A(4)

medical condition in a research participant, that does not necessarily have a causal relationship with protocol treatment. All adverse events for this protocol will be defined as those listed in the MSKCC Surgical Secondary Event Program. Any grade 3 or higher as determined by this database will be reported to the IRB.

A serious adverse event (SAE) is an undesirable sign, symptom or medical condition that is fatal or life-threatening

- results in persistent or significant disability/incapacity
- constitutes a congenital anomaly/birth defect
- requires prolongation of existing hospitalization, unless hospitalization is for:
 - elective or pre-planned treatment for a pre-existing condition that is unrelated to the indication under study and has not worsened since the start of study drug
 - treatment on an emergency outpatient basis for an event not fulfilling any of the definitions of a SAE given above and not resulting in hospital admission
 - social reasons and respite care in the absence of any deterioration in the patient's general condition
 - is medically significant, i.e., defined as an event that jeopardizes the patient or may require medical or surgical intervention to prevent one of the outcomes listed above

NOTE:

The following hospitalizations are not considered to be SAEs:

- Admission for a planned medical/surgical procedure
- Routine health assessment requiring admission for baseline/trending of health status (e.g. routine colonoscopy)
- Medical/surgical admission for purpose other than remedying ill health state which was planned prior to entry into the study; appropriate documentation is required in such a case
- Social reasons and respite care in the absence of any deterioration in the patient's general condition

All complications will be prospectively recorded. The hepatobiliary surgery service runs a biweekly meeting in which all complications are discussed and prospectively recorded into the Memorial Sloan-Kettering Surgical Secondary Events Program Database. At this meeting attendings discuss individual patients and assess the outcomes in order to record complications according to predefined criteria. **appendix 2 and 3**. Research personnel directly involved in the protocol will not influence this process.

A Hepatopancreaticobiliary research study assistant will query the Surgical Secondary Events Program Database at 30 days after each patient's operation and prospectively collect morbidity data for patients enrolled in the study.

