2.0 OBJECTIVES AND SCIENTIFIC AIMS

Primary objective:

- Evaluate the impact of goal-directed fluid management on the incidence of overall postoperative morbidity in patients undergoing liver resection.

Secondary Objective:

- Assess the impact of GDT compared to standard fluid therapy on the total time patients experience low cardiac output perioperatively (i.e. intraoperative and in the first 24 postoperative hours).
- Assess the impact of GDT compared to standard fluid therapy on the total volume of fluid given intraoperatively and during the first 72 hrs postoperatively.
- Assess the impact of GDT compared to standard fluid therapy on the requirement for blood transfusion.
- Compare the total dose (mcg/kg) of vasoactive agents used in the first 24 hrs between the standard management and GDT groups.
- Measure the difference in end-organ perfusion markers between GDT and standard therapy for fluid management.
- Assess the impact of GDT compared to standard fluid therapy on net fluid balance for the total admission time.
- Assess the impact of GDT compared to standard fluid therapy on the systemic inflammatory response.

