4.0 OVERVIEW OF STUDY DESIGN/INTERVENTION

4.1 Design

Prospective single-blinded randomized trial. Eligible patients will be consented for the trial prior to surgery. However randomization will not occur until the operating room. After the liver has been resected, intraoperative randomization will be done by envelopes. Preoperative preparation and induction will be standard for all patients. In the OR all patients will have an arterial line placed preinduction and baseline hemodynamic data recorded from the Edwards EV1000 system. In the study, all intraoperative fluid therapy will be managed with the standard LCVP anesthetic technique for hepatic resection, and then at the completion of the resection all fluid therapy will be managed according to randomization arm (Goal-directed fluid therapy-**appendix 1** compared to standard fluid management- see detail below) for reconstruction and closure. In the postoperative phase, management will be standardized for both arms as outlines below.

During low central venous pressure (LCVP) anesthetic technique for partial hepatectomy, intraoperative fluid balance is divided in to two phases (as previously published)⁸:

- Prehepatic resection (the first phase), starts at anesthesia induction and ends at the completion of parenchymal transection and hemostasis. This phase takes advantage of fluid restriction and the vasodilatory effects of anesthetic drugs to provide LCVP anesthetic management. Fluid boluses and/or vasoactive drugs are administered at the discretion of the anesthesia provider to maintain systolic blood pressure > 90 mm Hg and urine output > 25 ml/hr while keeping the cvp <5 mmHg (currently, the vast majority of our patients do not require central line placement for the performance of liver resections. Low central venous pressure is assessed by the surgeon's direct assessment of the distention of the vena cava at the time of surgery). Maintenance fluid is 1cc/kg/hr.

Prior to proceeding to the second phase the intraoperative fluid management after the hepatic resection, patients will be randomized to either

Goal-directed fluid therapy (**see appendix 1**)

Standard fluid management (**see appendix 1**).

MEMORIAL SLOAN-KETTERING CANCER CENTER IRB PROTOCOL

IRB#: 12-056 A(4)

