Adequacy of postoperative resuscitation will be determined by comparing end-tissue perfusion variables as well as inflammatory markers (a multiplex cytokine panel that includes IL-2, IL-4, IL-6, IL-10, IL-17, TNF α , and INF γ) before skin incision (as baseline), at the beginning of resuscitation phase, at time of completion of the case and the morning of the 2

MEMORIAL SLOAN-KETTERING CANCER CENTER IRB PROTOCOL

IRB#: 12-056 A(4)

first postoperative days. **See Table 2 – section 10.0 Evaluation during treatment/Intervention.** After evaluation of inflammatory response in the initial set of 20 randomized patients, it was determined that no statistically significant difference was likely to be found between the 2 randomization arms and the protocol was amended to discontinue the blood collections and cytokine analysis.

Continuous assessment of cardiac output as determined by the arterial waveform analysis, total fluid therapy, (crystalloid and colloid), units of pRBCs, total dose (mcg/kg) of each vasoactive agent, cumulative fluid balance and the incidence of overall 30-day postoperative complications will be recorded. These are defined in the MSKCC Adverse Events Program and organized by categories reflecting organ systems (listed below) and further subdivided into specific complications within those and graded as reflected in appendix 2. A detailed listing of complications and grading can be found at: <http://vssurpweb1/AdverseEvents>.

Categories

*None at 30 days post-op

Cardiovascular System

Endocrine System

Gastrointestinal System

General

Genitourinary System

Head and Neck

Hematologic or Vascular System

Infection

Metabolic

Musculoskeletal System

Nervous System

Pain

Pulmonary System

Wound or Skin

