14.0 BIOSTATISTICS

This is a randomized comparison of goal-directed compared to standard fluid management in patients undergoing liver resection. Primary endpoint is overall postoperative morbidity.

270 patients will be randomized 1:1 to the two arms. This sample size provides 80% power for detecting a 15% decrease in the proportion of overall postoperative complications (i.e regardless of grade of severity), assuming the standard arm will have a 30% complication rate (two-sided Type I error of 5%). It also allows for an interim analysis halfway through enrollment, using O'Brien-Fleming boundaries both for efficacy and futility. If $p \leq 0.005$ at the interim analysis enrollment will stop with the conclusion that goal-directed fluid management significantly decreases postoperative morbidity. If $p \geq 0.468$ at the interim analysis enrollment will stop with the conclusion that goal-directed fluid management does not significantly decrease postoperative morbidity. If $0.005 < p < 0.468$ then the trial will continue to full enrollment. With an approximate enrollment of 11 patients per month, accrual should be complete in 2 years.

Secondary endpoints will be compared between the two arms using the Wilcoxon rank-sum test, except for the categorical endpoints of blood transfusion and systemic inflammatory response, which will be compared using Fisher's exact test.

MEMORIAL SLOAN-KETTERING CANCER CENTER IRB PROTOCOL

IRB#: 12-056 A(4)

Since one of our main goals for this study is to establish what the individual amount of resuscitation is for each patient, tailored to their hemodynamic status, we decided to use their baseline value ± 2 standard variations as their homostatic stroke volume variation. An elevation above 2 standard deviations would be statistically unlikely to represent a normal variation of the measurement and will thus be considered a hemodincomically significant deviation from baseline.

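### The lactate and DO2 comparison leaves two pre-treatment values unused, which costs precision, and the sections that schedule these samples need reconciling

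*Combined protocol and SAP*

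**What the plan says.** Section 2.0 makes tissue perfusion a secondary objective: "Measure the difference in end-organ perfusion markers between GDT and standard therapy for fluid management". Section 12.0 repeats it as a secondary outcome.

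Section 10.0 names the markers as arterial lactate and DO2 and sets four times: before incision, which it labels baseline, then "at completion of the resection phase (intraoperatively), upon arrival to PACU (0 hours postoperatively), and on the morning of POD #1".

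Section 4.1 places allocation in the operating room: "After the liver has been resected, intraoperative randomization will be done by envelopes". The pre-resection phase "starts at anesthesia induction and ends at the completion of parenchymal transection and hemostasis", and the arms separate only afterwards: "Prior to proceeding to the second phase the intraoperative fluid management after the hepatic resection, patients will be randomized to either" of the two fluid strategies.

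Section 4.1 also gives a schedule for perfusion variables and the cytokine panel together. It starts before skin incision (again called baseline) and continues "at the beginning of resuscitation phase, at time of completion of the case and the morning of the 2" first postoperative days. It refers to Table 2 for detail. It then reports that blood collections and cytokine analysis were discontinued by amendment after the first 20 randomised patients were evaluated.

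Section 9.0 keeps patients in the PACU until the next morning. When they leave, "the arterial line will be removed upon transfer to the floor".

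On analysis, Section 14.0 says only: "Secondary endpoints will be compared between the two arms using the Wilcoxon rank-sum test", with an exception for two categorical endpoints. It names no time point, baseline, change score or covariate for lactate or DO2.

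**The concern.** Both arms receive the same low-CVP management until resection is complete. Lactate and DO2 at that point describe the patient and the operation so far, and cannot reflect the assigned fluid strategy. If they predict the PACU-arrival value, part of the between-patient spread at PACU arrival was already fixed before treatment. An analysis that leaves it in the error term is noisier than it needs to be, although the data to remove it are already being collected.

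An endpoint measured four times with no named time point also leaves the analyst to choose, after seeing the data, which comparison answers the objective.

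Finally, Sections 4.1 and 10.0 do not list the same sampling times. The difference matters most on POD 2, when by Section 9.0 the arterial line is already out.

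**Working it through.** **1. The plan's own figure.** The documents give no sample size, SD or target effect for lactate or DO2. The one figure is 270 patients for the primary endpoint (30% against 15%, two-sided 5%, 80% power). It reproduces:

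- Uncorrected: n per arm = [1.96·√(2·0.225·0.775) + 0.8416·√(0.30·0.70 + 0.15·0.85)]² / 0.15² = (1.1575 + 0.4889)² / 0.0225 = 120.5, so 121.
- Continuity-corrected: (120.5/4)·[1 + √(1 + 4/(120.5·0.15))]² = 133.5, so 134 per arm and 268 in total, against 270 stated.

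Nothing below changes it.

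**2. Sample times against allocation.**

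| Section 10.0 time | Position relative to randomisation | Can show an arm effect? |
|---|---|---|
| Before incision | Before | No |
| Completion of resection | Before, by the phase definitions | No |
| PACU arrival | After | Yes |
| Morning of POD 1 | After | Yes |

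Two of the four values are pre-treatment. The second is an inference: the resection phase ends at hemostasis and randomisation precedes the next phase, but no sentence says that the sample is drawn before the envelope is opened. The 30-minute tolerance stated with Table 2 concerns PACU and ward samples and does not settle this.

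**3. What adjustment is worth.** Assumptions, none from the documents: a true effect of 0.30 SD at PACU arrival, 135 per arm with complete data, a normal approximation, and correlation r between the pre-treatment and PACU-arrival values.

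- Residual variance = 1 − r².
- Power = Φ(0.30·√(135/2)/√(1 − r²) − 1.96), where 0.30·√67.5 = 2.465.

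| r | 1 − r² | 2.465/√(1 − r²) | Power |
|---|---|---|---|
| 0 (unadjusted) | 1.00 | 2.465 | 69% |
| 0.3 | 0.91 | 2.584 | 73% |
| 0.5 | 0.75 | 2.846 | 81% |
| 0.7 | 0.51 | 3.451 | 93% |

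The unadjusted row is a z-test. With normal data a Wilcoxon test scales the signal by √(3/π) = 0.977, so 2.465 × 0.977 = 2.408 and power is Φ(0.448) = 67%.

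**4. The two schedules side by side.**

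| Section 4.1 (perfusion variables and cytokines) | Section 10.0 (lactate and DO2) |
|---|---|
| Before incision | Before incision |
| Start of resuscitation | Completion of resection |
| Completion of the case | PACU arrival |
| POD 1 morning | POD 1 morning |
| POD 2 morning | None |

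The first four rows nearly match. The fifth does not. Section 4.1 derives cardiac output from the arterial waveform, and Section 9.0 removes the line on leaving the PACU, the morning after surgery. No source is therefore stated for arterial lactate or waveform-based DO2 on POD 2.

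**The case against.** The strongest reply is that an unadjusted Wilcoxon test of a post-randomisation value is valid under randomisation, that this is one of several secondary objectives, and that covariate adjustment is a choice about efficiency. All of that stands. The point concerns precision and specification, not bias. The size of the gain also rests on assumptions: at r = 0.3 it is only about 4 percentage points.

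Three stronger readings are tempting, and the documents do not support them.

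- A reader might infer that the plan has no baseline. Sections 4.1 and 10.0 both label the pre-incision sample as baseline. What is missing is any use of it, or of the value nearest randomisation, in Section 14.0.
- A reader might infer that the arms will be tested on pre-randomisation samples. Section 14.0 does not say so; that would be reading intent into silence.
- A reader might infer that the plan requires a POD 2 value that cannot be obtained. Section 4.1 does not name lactate or DO2, and its POD 2 time may belong to the cytokine panel. The lactate and DO2 rows of Table 2 are not legible in the text available. A separate arterial puncture is not ruled out for lactate. The passages show an unresolved conflict, not an impossibility.

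It is also fair to say that the order of the completion-of-resection draw and the envelope is inferred, and that the Section 4.1 counterpart, at the start of resuscitation, could fall just after allocation. The fix has to deal with that. Lastly, the amendment does not say whether the discontinued blood collections included lactate, although Section 10.0 still lists it.

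**Conclusion.** The point holds as one of precision and clarity. Two of the four Section 10.0 values are pre-treatment by the phase definitions, only two can carry an arm effect, and Section 14.0 neither names the time point to compare nor uses a pre-treatment value. The planned test is valid.

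Under the stated assumptions the forgone gain is small at r = 0.3 and substantial at r = 0.7. Without a correlation from the trial's own data, no single figure should be quoted. The illustration covers one marker at PACU arrival; with incomplete pairs the gain is smaller. POD 1 values may also be lost because Section 13.0 removes patients transferred to intensive care.

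The mismatch between Sections 4.1, 9.0 and 10.0 on POD 2 is real and supports reconciliation only.

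**What to change.** In Section 14.0:

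- Compare arms on lactate and DO2 at PACU arrival (main) and on the morning of POD 1 (supportive).
- Use ANCOVA on log lactate and on DO2, or a rank-based equivalent, with the completion-of-resection value as covariate.
- State that this sample is drawn before the envelope is opened, or at least before any arm-specific fluid. If that order cannot be assured, use the pre-incision value as covariate.

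Separately, reconcile Sections 4.1, 9.0, 10.0 and Table 2 so that one schedule applies to the perfusion variables. If a POD 2 value is meant, state its source. Say whether the amendment that stopped blood collections covers lactate.

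Cost: a few sentences. If lactate sampling continues as Section 10.0 lists it, no extra draws are needed. The small downside is reliance on a model and on complete paired samples, so the plan should also say how a missing covariate is handled. The primary endpoint and the 270 patients do not change.

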12.0 CRITERIA FOR THERAPEUTIC RESPONSE/OUTCOME ASSESSMENT

The null hypothesis is that GDT in patients undergoing liver resection does not alter the incidence of postoperative complications. A 15% decrease (from 30% to 15%) in the

MEMORIAL SLOAN-KETTERING CANCER CENTER IRB PROTOCOL

IRB#: 12-056 A(4)

incidence of 30-day complications will be considered clinically significant and will represent the primary outcome measure. The incidence of these will be assessed after each patient's postoperative visits.

Secondary outcomes include the impact of GDT on low cardiac output time, total volume of fluid used perioperatively, the requirement for blood transfusion, the total dose of vasoactive drugs, end-organ perfusion markers and the net fluid balance 48 hrs postoperatively.

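### The 30-day endpoint is extracted on day 30, but complications enter the database at a biweekly meeting, so late in-window events may not yet be recorded when it is read

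*Combined protocol and SAP*

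**What the plan says.** Section 10.0 defines postoperative complications as those "occurring on or after postoperative day 1 until postoperative day 30". Section 12.0 makes the incidence of 30-day complications the primary outcome, and Section 14.0 sizes the trial on 30% against 15%.

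The adverse-event text just before Section 12.0 describes how the data are obtained. The hepatobiliary service holds a "biweekly meeting in which all complications are discussed and prospectively recorded" in the institutional secondary-events database. Research personnel are kept out of that process. A study assistant will "query the Surgical Secondary Events Program Database at 30 days after each patient's operation" to collect morbidity for enrolled patients.

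Section 12.0 describes the timing differently: "The incidence of these will be assessed after each patient's postoperative visits". It gives no visit dates.

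Section 4.1 lists a category for having no complication at 30 days. It does not say when that category is entered or whether the query waits for it.

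**The concern.** The window closes on the day the source is read, yet entry into the source depends on a periodic meeting. An event between the last meeting before day 30 and day 30 belongs to the endpoint but, on the process as written, may not be in the database at the query. The same applies to a complication first noted at a visit on or after day 30 whose onset was inside the window.

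The exposed events are late ones, many presumably after discharge. If they are not picked up later, both arms' rates are understated and the absolute difference, on which the trial is sized, shrinks. The same extraction would feed the halfway interim analysis, where p ≥ 0.468 stops enrolment.

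**Working it through.** **Inputs from the documents.** Rates 30% and 15%, two-sided 5% level, 80% power, 270 patients at 1:1, or 135 per arm (Section 14.0). Window POD 1 to 30 (Section 10.0). Query at day 30 and biweekly meeting (adverse-event text).

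**Inputs that must be assumed.** The documents give no timing of complications and do not define biweekly. I take the first complication's onset as exponential with mean m = 5, 7 or 10 days (before truncation), truncated to days 1–30. The gap between the last meeting and day 30 is uniform on 0 to L, with L = 14 days (every two weeks) or 4 days (the longer gap with two meetings a week). An event is recorded at the first meeting after onset. The endpoint is any complication, so a patient is misclassified only if the first one falls in the gap.

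**Step 1: the plan's sample size.** With d = 0.15 and mean rate 0.225:

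- Uncorrected n per arm = [1.960·√(2·0.225·0.775) + 0.8416·√(0.30·0.70 + 0.15·0.85)]² / 0.15² = 120.5, so 121 (242 in all).
- With continuity correction: (120.5/4)·[1 + √(1 + 4/(120.5·0.15))]² = 133.5, so 134 (268 in all), close to the stated 270.

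Section 14.0 names neither the correction nor the primary test, so both versions are carried forward.

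**Step 2: power with complete capture.** Power = Φ{[d − 1/n − 1.960·√(2·p̄·(1−p̄)/n)] / √[(p₁(1−p₁) + p₂(1−p₂))/n]}, dropping 1/n for the uncorrected version. At n = 135 this is 80.5% corrected and 84.3% uncorrected.

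**Step 3: share missed.** Averaged over the gap,

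f = [(m/L)·e^(−30/m)·(e^(L/m) − 1) − e^(−30/m)] / [e^(−1/m) − e^(−30/m)].

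For m = 7, L = 14: (0.5·0.01376·6.389 − 0.01376) / (0.8669 − 0.0138) = 0.0302/0.8531 = 3.5%.

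**Step 4: effect.** Both rates are multiplied by (1 − f), so the difference becomes 15(1 − f) points.

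| Meetings | m (days) | Average f | Observed rates | Power, corrected | Power, uncorrected |
|---|---|---|---|---|---|
| complete capture | – | 0 | 30.0% v 15.0% | 80.5% | 84.3% |
| every two weeks | 5 | 1.4% | 29.6% v 14.8% | 79.7% | 83.7% |
| every two weeks | 7 | 3.5% | 29.0% v 14.5% | 78.5% | 82.6% |
| every two weeks | 10 | 6.9% | 27.9% v 14.0% | 76.5% | 80.9% |
| twice a week | 5 | 0.2% | 29.9% v 15.0% | 80.4% | 84.2% |
| twice a week | 7 | 0.6% | 29.8% v 14.9% | 80.2% | 84.1% |
| twice a week | 10 | 1.3% | 29.6% v 14.8% | 79.8% | 83.7% |

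Even spacing of 3.5 days brings the lowest twice-weekly loss to about 0.1%.

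**Step 5: interim.** With about 67 per arm at 30% v 15%, the normal-approximation chance of p ≥ 0.468 is 8.2%. At the two-week average losses it is 8.5%, 9.0% and 9.7%.

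**The case against.** The strongest objection is that nothing is shown to be lost. A reader might infer from the day-30 query that late events drop out for good, but no section says the query is one-time or final, that data lock then, or that later entries with an in-window onset are excluded. The database is a standing service record, so an event entered at the next meeting could still be retrieved. Section 16.1 plans routine checks for missing data and of the extent of follow-up, and Section 12.0 can be read as assessment beyond one fixed query. The opening of the adverse-event section and part of Table 2 are missing from the text available, so a catch-up rule there cannot be excluded. This stands, and it limits the point to a risk.

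A reader might also say that the endpoint really measures 16- to 30-day morbidity. That needs two-week meetings and a final query, and the documents establish neither.

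A third tempting step is to apply the worst meeting phase to everyone. With two-week meetings, patients whose day 30 falls just before a meeting lose about 5%, 10% or 18% for the three onset means. Meeting phase varies between patients, so the averages are the relevant figures.

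It may further be said that a patient without complications cannot be told from one not yet discussed. The category in Section 4.1 may make that distinction, though its timing is unstated.

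Finally, the process is the same in both arms. An equal proportional loss leaves the relative risk unchanged, and no mechanism favouring one arm is shown. What survives is that the written rule reads the source before its entry process can have caught up, and that no remedy is written in the text available.

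**Conclusion.** The point holds as a gap in the extraction rule. Followed literally, it can miss events inside the 30-day window, and it is not reconciled with the visit-based wording of Section 12.0.

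The size is small to modest. With two-week meetings and the assumed onset patterns, power falls by about 1 to 4 percentage points. On the continuity-corrected basis that comes close to 270, there is almost no slack, so even the mildest two-week case dips just under 80%. On the uncorrected basis all three stay above it. With twice-weekly meetings the effect is negligible. The chance of stopping at the interim for futility rises by at most about 1.5 points.

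These figures assume that the day-30 query is the last, that loss is equal in both arms, and that first complications are front-loaded. The expected consequence is under-ascertainment and a smaller absolute difference. Bias between arms or an inflated type I error has not been demonstrated.

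**What to change.** Amend the adverse-event text so that the query, or a stated repeat query, runs after the first complication meeting that follows both day 30 and the postoperative visit at which 30-day status is assessed. Day 45 would serve if that visit falls by day 30, since with two-week meetings the next one comes no later than day 44. Count events by onset date within POD 1–30. Also:

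- define biweekly;
- name the visit meant in Section 12.0 and align the two sections;
- state a lock date, and apply the same matured extraction to every patient in the interim and final analyses.

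The cost is a few sentences of protocol text and no extra patients. Each patient's data, and so the interim and final data sets, close about two weeks later.
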